# 19B2. Statistical analysis of inflammation and endothelial cell studies for Combination therapy pilot study

The objective of this matched case-control study is to determine the activity profile of the combination of anakinra and atorvastatin in the treatment of KD subjects with CAA. Measures of inflammation and endothelial cell function will be compared to that of matched controls via paired statistical tests (e.g. McNemar's test for categorical outcomes or the paired t-test for continuous outcomes). Non-parametric alternatives will be considered only if distributional assumptions are violated.

**Control Group:** Controls will be chosen from the >600 subjects with data in our web-based data repository in REDCap. Controls will be matched to study patients based on age, sex, illness day at diagnosis, and baseline Z score.

Analysis: Each marker will be initially summarized descriptively and analyzed individually. Separate multivariable mixed effects regression modeling for clustered data (to account for the case-control paired nature of samples) will be used to characterize the markers of treated subjects versus matched controls to adjust for any known confounders and additional time points (baseline, 48 hours, 2 weeks, and 6 weeks). In addition, any covariate at the individual level that is simultaneously unbalanced and associated with the outcome will be included in the model. Covariates of interest include demographic variables (e.g., ethnicity, Illness Day at diagnosis, response to IVIG therapy). Permutation tests may be implemented to verify that valid p-values will be obtained even if model assumptions are not correct. Note that the mixed model seamlessly accommodates different times of measurement (e.g. 48h and 2-week time points) as well as missed measurements and data from subjects who are lost to follow-up. A corresponding Generalized Estimating Equations (GEE) model will be used as the sensitivity analysis method. To determine the "best" or "set of best" markers that have the greatest improvement from baseline in anakinra/atorvastatin-treated patients, ROC and AUROC analysis will be considered to choose the best of set markers for a future clinical trial. In the event that there is high multicollinearity amongst the markers, we will adopt the "glmpath" approach. which is based on Least Angle Regression (LARS) methods to select the best biomarkers.(Park 2007)

Measures of transcript abundance will also be analyzed via RNAseq. The R software (version 3.0.2) and Bioconductor package in R will be used for the analysis. For coronary outcomes as assessed by echocardiography, we will compare the delta Z scores (baseline minus 2-weeks and 6-weeks) between anakinra subjects and matched controls. A GEE model will be used as the sensitivity analysis method. Since this is a pilot study, no adjustments for multiple comparisons will be made for biomarker analyses. P-values less than 0.05 will be considered statistically significant. All statistical analyses will be performed in R version 3.2.0 (www.r-project.org/).

Missing data assumptions: The proposed mixed-effects regression model is consistent under the assumption that the outcome data are "missing at random" (MAR), that is, mixed models with a random effect assume only that the probability that an outcome is missing depends on observed outcomes. GEE models, which are proposed as a sensitivity analysis, assume that the outcome data are "missing completely at random", that is, that the probability that an outcome is missing does not

depend on any previous, present or succeeding value of the outcome. This will enable us to assess the impact of the missing data mechanism on statistical inferences drawn from these models.

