### 12E. Maximum Tolerated Dose for Phase I/IIa anakinra study

The Maximum Tolerated Dose (MTD) will be defined as the highest dose of anakinra studied at which no more than one in six patients experiences a DLT during the 6 weeks of treatment. Subjects will be enrolled at the maximum tolerated dose until a total of 30 subjects have been enrolled in the study. Given the 3+3 design of the study, if there is a DLT then a total of 6 subjects will enrolled per dose level. If we reach the 8 mg/kg/day dose level, then up to a maximum of 12 subjects will be enrolled at a dose level below the MTD (4 mg/kg and 6 mg/kg). This leaves 18 subjects treated at the MTD if the third dosing level is reached. If there are no DLTs at the first two levels, then 3 subjects will be enrolled at the MTD. Thus, between 18 and 24 subjects will be enrolled at the MTD if the 3rd dose level is reached.

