# 15. Sample Size

#### 15A. Sample size for Phase I/IIa anakinra study

A study population of a minimum of 18 KD patients treated with the MTD of anakinra (See Section 11E for subjects at MTD) and 18 historic matched controls from the Kawasaki Research database will have 80% power based on a two-sided, paired t-test to compare change scores from baseline between cases and controls with alpha set to 0.05 to detect a minimum difference for the change score for several transcript levels of the IL-1 family, including IL-1RAP (pooled SD of 3.2 and corresponding difference of 2.2) and IL-1R1 (pooled SD of 8 and corresponding difference of 5.6). The effect sizes are based on relevant changes that were found in the largest KD microarray study done to date (Hoang 2014).

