#### 15B. Sample size for Combination therapy pilot study

This study is not powered to show a difference in echocardiographic measurements or treatment response compared to controls. Instead, the sample size will be determined based on detectable differences in inflammatory markers and readouts from *in vitro* EC studies. A sample size of 10 KD patients treated with anakinra/atorvastatin combination therapy vs 10 matched historical controls treated with standard therapy alone will have 80% power based on a two-sided, paired t-test with alpha set to 0.05 to detect an effect size of 89% in the mean change of EC homeostasis (i.e. markers of EndoMT) and inflammasome activation (i.e. TIFA, NLRP3) using the *in vitro* EC culture system.

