The above approach will be repeated for the other markers. That is, multi-level mixed effects regression models analogous to the above methodology will be applied for other markers: Levels of high sensitivity (hs) CRP, alpha-1 antitrypsin, TNFaR1 and R2, IFNg, IL-1 RAP, IL-1R1 and R2, MMP9, caspase-1, IL-6R, IL-18RAP, IL-12, IL-2, TGFb and IL-10.

Measures of transcript abundance will also be analyzed via microarray analysis. Data will be preprocessed first and then microarray analysis procedures will be used to measure abundance. The R software (version 3.0.2) and Bioconductor package in R will be used for the analysis. For coronary outcomes as assessed by echocardiography, we will compare the delta Z scores (baseline minus 2weeks and 6-weeks) between anakinra subjects and matched controls. A GEE model will be used as the sensitivity analysis method. Since this is a safety and early efficacy study, no adjustments for multiple comparisons will be made for biomarker analyses. P-values less than 0.05 will be considered statistically significant. All statistical analyses will be performed in R version 3.2.0 (www.rproject.org/). Similarly, analyses will be repeated on all subjects to characterize any dose-activity relationship, adjusting for dosage as a covariate in the model.

To determine the "best" or "set of best" markers that have the greatest improvement from baseline in anakinra-treated patients, ROC and AUROC analysis will be considered. In the event that there is

high multi-collinearity amongst the markers, we will adopt the "glmpath" approach, which is based on Least Angle Regression (LARS) methods to select the best biomarkers (Park 2007).

Missing data assumptions: The proposed mixed-effects regression model is consistent under the assumption that the outcome data are "missing at random" (MAR), that is, mixed models with a random effect assume only that the probability that an outcome is missing depends on observed outcomes. GEE models, which are proposed as a sensitivity analysis, assume that the outcome data are "missing completely at random", that is, that the probability that an outcome is missing does not depend on any previous, present or succeeding value of the outcome. This will enable us to assess the impact of the missing data mechanism on statistical inferences drawn from these models.

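### Marker selection by ROC/AUROC (or glmpath) has no stated correction for selection, so the best of several null markers can look useful, mainly in the 10-case combination pilot

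*Combined protocol and SAP*

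**What the plan says.** Both studies want to find the marker or set of markers that improves most from baseline in treated patients. For Phase I/IIa, 19B1 says that "ROC and AUROC analysis will be considered". For the combination pilot, 19B2 goes further and gives the purpose: "ROC and AUROC analysis will be considered to choose the best of set markers for a future clinical trial". In both, glmpath (least angle regression) replaces this if the markers are highly collinear. For Phase I/IIa the link to a later trial is in section 8A1, which says the activity results will help to fix Phase III endpoints.

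Both sections state that biomarker analyses will not be adjusted for multiple comparisons and that p below 0.05 counts as significant. Neither mentions cross-validation, optimism correction, a hold-out set, an AUROC interval or threshold, or a tuning rule for glmpath. The only resampling named is an optional permutation check of the mixed-model p-values. The two classes that the ROC curve should separate are not defined.

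**The concern.** An AUROC computed in the subjects who were used to pick the winning marker is biased upward. The bias grows with the number of candidates and shrinks with the number of subjects, and here there are many candidates and few subjects. Because 19B2 ties the selection to a future trial, a chance marker with a respectable AUROC could be carried forward as an endpoint. An uncorrected figure would give the reader no sign of this.

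**Working it through.** **Group sizes from the plan.** Section 15B gives "A sample size of 10 KD patients treated with anakinra/atorvastatin combination therapy vs 10 matched historical controls treated with standard therapy alone", with "80% power based on a two-sided, paired t-test with alpha set to 0.05". Its stated effect size is 89%. Reading that as a standardized difference of 0.89 (an assumption), n = ((1.960 + 0.842)/0.89)² = 9.9, so 10 pairs reproduce by the normal approximation. The paired t-test itself gives 70.8% power at 10 pairs and needs 12; that is a separate matter. Section 15A gives "A study population of a minimum of 18 KD patients treated with the MTD of anakinra" and "IL-1RAP (pooled SD of 3.2 and corresponding difference of 2.2". With d = 2.2/3.2 = 0.6875 and 18 pairs, the paired t-test has 78.5% power; with 5.6/8 = 0.70 for IL-1R1 it has 79.9%. So 15A reproduces closely. Section 12E expects that "between 18 and 24 subjects will be enrolled at the MTD" if the third dose level is reached.

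**Other control numbers.** Section 18A plans two controls per case. Section 18B plans 20 standard-treatment controls, plus 10 on atorvastatin and 10 on anakinra. I therefore ran both ratios.

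**Candidate counts (my count).** For the pilot: 9 plasma markers (7G2, 18B), 18 with the same analytes as transcripts, and about 25 with at least 7 endothelial readouts (18B). For Phase I/IIa: 16 protein markers (19B1), before any transcripts.

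**Formula.** For marker k with n1 treated subjects and n0 controls, AUROC_k = (1/(n1·n0)) Σ Σ [1(x > y) + ½·1(x = y)]. Either direction uses max(AUROC, 1 − AUROC); improvement only uses the AUROC itself. The apparent result is the maximum over k.

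**Hand check, 10 vs 10.** The null SD of one AUROC is √((n1 + n0 + 1)/(12·n1·n0)) = √(21/1200) = 0.132. A value of 0.80 lies 0.30/0.132 = 2.27 SD from 0.50, so one pre-specified marker gets there in about 2.3% of trials (either direction). For 9 independent markers, 1 − 0.977⁹ = 19%.

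**Simulation.** All markers null, normal data, treated vs control, matching ignored, 20,000 runs. Each cell runs from inter-marker correlation 0 to 0.7.

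| Treated vs control | Markers | Mean best AUROC, either direction | Chance ≥ 0.80, either direction | Chance ≥ 0.80, improvement only |
|---|---|---|---|---|
| 10 vs 10 | 9 | 0.74–0.70 | 19–12% | 10–6% |
| 10 vs 10 | 18 | 0.78–0.73 | 35–17% | 19–9% |
| 10 vs 10 | 25 | 0.79–0.74 | 45–20% | 26–10% |
| 10 vs 20 | 18 | 0.74–0.69 | 12–6% | 6–3% |
| 18 vs 18 | 16 | 0.70–0.66 | 2.5–1.4% | 1.3–0.7% |
| 18 vs 36 | 16 | 0.67–0.64 | 0.4–0.3% | 0.2–0.1% |
| 24 vs 24 | 16 | 0.67–0.64 | 0.4–0.3% | 0.2–0.1% |

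Counting improvement only, the mean for 10 vs 10 with 9 markers is 0.70 at correlation 0 and 0.67 at 0.3. Separate runs of 8,000 gave 18–20% for the first row at those two correlations.

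**glmpath.** I used a lasso path stopped at three or fewer markers as a stand-in (400 runs, all null, 10 vs 10). At correlation 0 the apparent AUROC averaged 0.81, 0.85 and 0.87 for 9, 18 and 25 markers; at 0.5 it averaged 0.79, 0.83 and 0.85. In new data it averaged 0.48–0.51. Shrinkage does not remove the optimism.

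**Does correction work?** For 10 vs 10 with 9 null markers, counting improvement only, a bootstrap that resamples matched sets and repeats the selection lowers the mean from 0.67–0.70 to about 0.56–0.57. A within-set max-statistic permutation test held its 5% level. With independent markers and either direction, the 5% cutoff for the best AUROC is about 0.85 for 9 markers, against 0.76 for one pre-specified marker. Leave-one-set-out AUROC centres on 0.50, but its SD is 0.24 and its 5–95% range is about 0.1 to 0.9. With one true marker (d = 0.89) it averages only 0.63, with a range of 0.2 to 1.0.

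**The case against.** The strongest reply is that the plan commits to little. ROC analysis is only to be considered and glmpath is conditional. A reader might infer that AUROC will certainly be computed uncorrected in the selection sample, or that it will ignore the matching. The documents support neither reading: no ROC computation is described, and the same sections use paired tests and clustered mixed models. What stands is that selecting the best markers is a stated aim and no correction is named, so nothing in the plan prevents an uncorrected figure.

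The figures also depend on a treated-vs-control contrast. If the ROC separates samples before and after treatment, they do not apply as calculated. That is a reason to define the classes.

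A reader might also infer that Phase I/IIa is as exposed as the pilot. It is not: 18 is a minimum, 18A plans 1:2 matching, and a best null marker then almost never reaches 0.80.

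Finally, the work is exploratory, safety is the primary outcome (7F1, 7F2), and each marker is also analysed individually. This limits the importance of the point but does not remove it. The individual tests are unadjusted as well: with 9 independent null markers, the chance of at least one p below 0.05 is 1 − 0.95⁹ = 37%. Exploratory status can excuse unadjusted p-values, but it does not make an inflated AUROC a sound basis for choosing a later trial's markers.

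**Conclusion.** The concern holds as a gap in specification with a material effect in the combination pilot and a smaller one in Phase I/IIa. With 10 vs 10 and 9 null markers, the best apparent AUROC averages about 0.70–0.74 in either direction and reaches 0.80 in roughly one trial in eight to one in five (6–10% for improvement only). Counting transcripts and endothelial readouts as candidates makes this worse; using 20 controls makes it better. In Phase I/IIa a null marker can still average 0.64–0.70, but 0.80 is rare.

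These sizes assume a treated-vs-control contrast, normal data, no allowance for matching, my marker counts, and correlations of 0 to 0.7; the documents give no values for the last two. The consequence falls on marker choice for a later trial. The documents give no ground for reading it as a threat to the safety conclusions.

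**What to change.** In 19B2, and likewise in 19B1:

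- State the two classes that the ROC separates, the time point and the full candidate list.
- Repeat the whole selection (AUROC ranking or glmpath, including tuning) inside a bootstrap that resamples matched sets.
- Report the apparent AUROC beside the optimism-corrected AUROC with an interval, the selection frequencies, and a within-set max-statistic permutation p-value.
- Label the chosen markers hypothesis-generating.
- Do not rely on leave-one-set-out AUROC alone with 10 sets; it is too variable.

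The cost is some extra code and no new data. Reported AUROCs will be lower and their intervals wide. The bootstrap leaves a small residual optimism (about 0.55–0.57 under the null instead of 0.50). The correction mainly changes how strong the evidence is said to be, not which marker ranks first, so the label and the selection frequencies are needed as well as the corrected number.

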# 20. Data and Safety Monitoring

#### 20A. Data and Safety Monitoring Board (DSMB) for Phase I/IIa anakinra study

As a first step in assuring the safety of subjects participating in this trial, monthly conference calls with the study nurse, PI, and co-investigators will be conducted to discuss progress of the trial and possible safety issues. Safety and clinical data will be tabulated and presented to the PI and co-investigators by the study biostatistician for discussion prior to opening the next dose level. The DSMB, a panel consisting of outside experts, including one clinician with expertise in KD, a pharmacologist, and a biostatistician, in collaboration with the Study Investigators, will pre-specify a plan for evaluating the data on a periodic basis and will set up pre-specified stopping rules for safety.

# 20B. Data and Safety Monitoring Plan (DSMP) for Combination therapy pilot study

As this is a study that involves children and the investigators must protect this vulnerable population, a DSMP has been established. To assure the safety of subjects participating in this trial, Drs. [name] and [name] will meet after enrollment of every 2 subjects to discuss progress of the trial and possible safety issues. Safety and clinical data will be tabulated and presented by the biostatistician to the investigators after five subjects have been enrolled and at the end of the study. An earlier meeting can be convened by [name], [name] or [name] if safety questions or other unanticipated problems arise.

The UCSD IRB, FDA, Pfizer and Sobi Pharmaceuticals will be immediately notified (within 48h) of any UPRs. For anticipated SAEs and AEs, the UCSD IRB will receive a report as per their reporting guidelines.

# **Appendix A:** Preparation of Anakinra (Kineret®) in the Hospital for Doses < 20 mg

The following protocol is completed using a single dose, pre-filled syringe of commercially available Kineret® (100 mg/0.67ml syringe) by a pharmacist or pharmacy technician who is gowned and gloved, and is wearing a cap, face mask, and shoe covers.

- 1. Aseptically transfer the anakinra directly into a sterile one ml syringe in an ISO Class 5 IV hood located in the hospital inpatient pharmacy IV Class 10,000 clean room.
- 2. The prepared dose syringe is then capped and labeled and given a 4-hour expiration under 2-8C refrigerated.

